PGA	patient's global assessment of disease severity
PP	per protocol population
REB	Research Ethics Board
SAE	serious adverse event
SAP	Statistical Analysis Plan
SBP	systolic blood pressure
SD	standard deviation
SEM	standard error of the mean
SMC	Safety Monitoring Committee
SOP	standard operation procedure

Abbreviation	Definition
TEAE	treatment-emergent adverse event
WBC	white blood cell
WOMAC	Western Ontario and McMaster Universities Arthritis Index

1 INTRODUCTION

The sole starting material of Ampion, human serum albumin (HSA), has a long history of clinical use as a colloid replacement therapy, dating back over 60 years. Currently, HSA is approved for intravenous administration for the indications of hypovolemia, hypoalbuminemia, prevention of central volume depletion after paracentesis due to cirrhotic ascites, ovarian hyperstimulation, adult respiratory distress syndrome (ARDS), acute nephrosis, hemolytic disease of the newborn and burns. In addition to its effects on oncotic pressure, HSA has pharmacological effects including decreased inflammation ([Quinlan 2005](#)), decreased vascular permeability ([Evans 2002](#)) and has no adverse effect on cardiac safety ([Vincent JL 2004](#)). The low molecular weight (< 5 kilodalton (kDa)) ultrafiltrate of 5% HSA, Ampion, is being developed as an intra-articular (IA) injection to provide relief for the pain due to severe osteoarthritis of the knee (OAK).

There are no currently FDA-approved drugs for the indication of pain from severe (Kellgren Lawrence [KL] Grade 4) OAK, for which Ampion is indicated. The active components in Ampion, aspartyl-alanyl diketopiperazine (DA-DKP), N-acetyl tryptophan (NAT), and caprylic acid (Caprylate), play a role in Ampion's biological activity and have been shown to reduce pro-inflammatory cytokine tumor necrosis factor-alpha (TNF α). DA-DKP is naturally present in human serum and is a cyclized dipeptide derived from the two N-terminal amino acids of albumin, aspartic acid and alanine. These amino acids are cleaved by a dipeptidase, and the resulting dipeptide is cyclized to form a diketopiperazine (aspartyl-alanyl diketopiperazine or DA-DKP). The formation of DA-DKP occurs during the HSA pasteurization process ([Bar-Or 2013](#)). The two other active components, NAT and Caprylate, are added during the manufacture of pharmaceutical HSA as stabilizers to protect albumin from heat denaturation and oxidation.

In vitro nonclinical studies, which use cellular models designed for the study of osteoarthritis, evaluate the role of Ampion in regulating inflammatory responses with cytokine tumor necrosis factor-alpha (TNF α), and other inflammatory markers, in immune cells (peripheral blood mononuclear cells, monocytes, macrophages), and support the clinical application of Ampion. A high-level summary of these studies is shown in [Table 1.1](#).

Table 1.1 Summary of Ampion nonclinical studies

Study Objective	Summary of Findings
Anti-inflammatory effects of HSA and DA-DKP (TNF α , IFN γ)	HSA inhibited the production of pro-inflammatory cytokines (IFN γ , TNF α) in activated immune cells; however, when the low-molecular weight ultrafiltrate was removed from HSA, no anti-inflammatory effects were observed. DA-DKP was detected in HSA from multiple vendors, and different concentrations of synthetic DA-DKP (25-500 μ M) were shown to inhibit TNF α release in a dose-dependent manner. This study identified early anti-inflammatory properties of Ampion (< 5 kDa ultrafiltrate of HSA) and of the active component DA-DKP. These results were published in the journal of Critical Care Medicine (Bar-Or 2006).

Study Objective	Summary of Findings
DA-DKP activity on cytokine production (TNF α , IFN γ , IL-8)	DA-DKP decreased production of pro-inflammatory cytokines (IFN γ , TNF α) in T-lymphocytes. DA-DKP also increased phosphorylation of the GTPase Rap-1, which in turn, decreased phosphorylated transcription factors involved in the regulation of TNF α and IFN γ gene transcription. Release of pro-inflammatory cytokine (IL-8) was not impacted by DA-DKP, suggesting that DA-DKP induction of active Rap-1 impacted the phosphorylation of only selected transcription factor pathways and was not a global effect. These results were published in the Journal of Trauma, Injury, Infection, and Critical Care (Shimonkevitz 2008)
Ampion anti-inflammatory activity (TNF α inhibition)	Ampion inhibited pro-inflammatory cytokine TNF α in activated immune cells by an average of 39%. Individual components contribute to activity: DA-DKP (100 μ M) 17% TNF α inhibition, NAT (3.0 mM) 17% TNF α inhibition, and Caprylate (0.6 mM) 19% TNF α inhibition and is published in the Journal of Immunoassay and Immunochemistry (Thomas 2016).
Dose responses of Ampion and individual components (TNF α inhibition).	Ampion and its components have been shown to inhibit TNF α in a dose-dependent manner in activated immune cells (IND 15345).

This *in vitro* data translates to *in vivo* use in humans, as it has been reported that synovial levels of TNF α correlate directly with Western Ontario and McMaster Universities Arthritis Index (WOMAC) measures of pain, stiffness, and functional disability, while other studies have reported that TNF α levels are associated with pain while standing ([Stannus 2013](#)).

1.1 Study Drug

Ampion is the < 5 kDa ultrafiltrate of 5% HSA.

1.2 Background to the Disease

Osteoarthritis (OA) remains a leading contributor to global disability, with both hip and knee OA accounting for over 17 million years lived with disability ([Cross 2014](#)). OA is the most common form of arthritis and affects up to 38 million adults in the US alone. OA is caused by inflammation of the soft tissue and bony structures of the joint which worsens over time and leads to progressive thinning of articular cartilage, narrowing of the joint space, synovial membrane thickening, osteophyte formation and increased density of subchondral bone. These changes eventually result in chronic pain and disability and deterioration of the joint and may require eventual surgery for total joint replacement. OA of the knee is defined in stages as noted by Kellgren-Lawrence (KL) grading: Grade 0 (normal knee; no osteophytes or joint space narrowing), Grade 1 (possible osteophytic lipping and doubtful narrowing of joint space), Grade 2 (definite osteophytes and possible narrowing of joint space), Grade 3 (moderate multiple osteophytes, definite narrowing of joint space and some sclerosis, and possible deformity of the bone ends) and Grade 4 (large osteophytes, marked narrowing of joint space, severe sclerosis, and definite deformity of bone ends).

The pain associated with OA is now thought to be multifactorial. The pathogenesis of pain from OA is comprised of both nociceptive and neuropathic pain pathways resulting from severely damaged cartilage, exposed subchondral bone, joint innervation, and less defined pathways including the synovium. The balance between nociceptive and neuropathic pain shifts towards

neuropathic pain as the severity of the condition increases ([Akinci 2016](#)). The multifactorial nature of the pain of OA may make pain control more difficult, particularly in patients with severe OAK (KL 4). Patients with severe OAK have few treatment options for pain management. Difficult-to-treat pain conditions, such as severe OAK, are a challenge for both medical doctors and patients. FDA has acknowledged an unmet medical need for patients with severe OAK.

The presence of synovitis in KL 4 patients indicates active ‘inflammatory’ disease process. These findings were supported with a linear observation of an increasing trend correlated with the severity of synovitis related to advancing KL grades. Additionally, KL 4 patients were shown to have lesions that fluctuate with pain (i.e., fluctuating bone marrow lesions and synovitis) related to a high grade of cartilage loss in KL 4 patients ([Guermazi 2015](#)). These findings were further supported using a unique *in vivo* imaging technique that detected activated and not resting macrophages ([Kraus 2016](#)). In a patient cohort that included patients with severe (KL 4) OAK, the quantity of knee-related activated macrophages was statistically associated with more severe knee pain and radiographic severity of OAK.

These data demonstrate that greater macrophage mediated inflammation is a cause of more severe pain in KL 4 OAK and provides a rationale whereby Ampion, which has demonstrated *in vitro* anti-inflammatory and anti-macrophage activity, may mediate symptomatic relief in this patient group. These data further demonstrate the need to examine patients by disease severity and supply treatment options for severely diseased patients ([Guermazi 2015](#)). Ampion has shown anti-inflammatory activity *in vitro* against macrophages, monocytes, and immune cells ([Bar-Or 2015](#), [Frederick 2016](#), [Thomas 2016](#), [Thomas 2016b](#)).

1.3 Previous Human Experience

In addition to the extensive HSA clinical experience, the sole starting material of Ampion, the Company has completed numerous clinical studies to evaluate the effect of Ampion in adults with OAK. These studies are summarized in Section 1.5.

1.4 Preclinical Data

1.4.1 Pharmacology Studies

In vitro pharmacology studies demonstrated that the low molecular weight ultrafiltrate of pharmaceutical preparations of HSA, and the cyclized dipeptide, DA-DKP, contained in that filtrate have a range of anti-inflammatory properties, which may be expected to ameliorate the symptoms of inflammation, including pain, in humans ([Bar-Or 2006](#)). Further, *in vitro* studies support anti-inflammatory properties for the < 5 kDa ultrafiltrate of HSA (Ampion) and its components (DA-DKP, NAT, Caprylate) with the reduction of pro-inflammatory cytokines ([Shimonkevitz 2008](#), [Thomas 2016](#), [IND 15345](#)). No pharmacokinetics studies were performed as the plasma levels of the constituents of the < 5 kDa preparation, including the active components (DA-DKP, NAT, Caprylate), after intra-articular (IA) injection of a therapeutic dose in humans or in laboratory animals would be below the limits of detection. For more information, consult the Investigator Brochure.

1.4.2 Toxicity and Safety Studies

HSA and other components of serum albumin preparations are species specific and may be expected to be immunogenic if repeatedly injected into non-human species, even at very low concentrations. For this reason, it was not possible to perform formal toxicological studies in animals.

1.5 Clinical Experience

Ampio has conducted multiple clinical studies to evaluate the treatment effect and safety of Ampion in subjects with OAK. Ampion has been administered across six clinical studies as a single IA injection or as three IA injections administered every two weeks. Four single-dose pivotal Phase 3 studies, two multi-dose studies, and one multiphase single-dose Phase 1b study have been completed. An overview of the efficacy studies is provided in the [Table 1.2](#).

For the clinical development program, all patients were required to have x-ray findings demonstrating KL 2, 3, or 4 disease severity. All studies enrolled patients with KL 4 disease. In addition, eligible subjects had at least moderate pain at Baseline (defined as a score of at least 1.5 on the WOMAC Index 3.1, as measured by the 5-point Likert pain subscale at screening) in the study knee, which was to have been symptomatic for greater than six months with a clinical diagnosis of OA confirmed by radiological evidence. The clinical effects of treatment on OA pain were evaluated during clinic visits, with phone call follow-ups according to the study visit schedule.

Table 1.2 Summary of the Studies Conducted with Ampion Administered as an Intra Articular Injection to the Knee

Study	Phase	N	N: KL 2, 3, 4	Route	Primary outcome	Primary endpoint	Additional outcomes	Test product
Single-Injection Phase 3 Studies in Support of Efficacy & Safety								
AP-003-A	3	329	115 / 139 / 75	Single IA injection	WOMAC A pain, 5- point Likert scale	Week 12	WOMAC B WOMAC C PGA OMERACT -OARSI Rescue analgesia	Ampion, 4 mL and 10mL
AP-004	3	538	133 / 195/ 210	Single IA injection	WOMAC A pain, 5- point Likert scale	Week 12	WOMAC C PGA WOMAC A pain over 12 weeks	Ampion, 4 mL

Study	Phase	N	N: KL 2, 3, 4	Route	Primary outcome	Primary endpoint	Additional outcomes	Test product
AP-003-C	3	168	0 / 0 / 168	Single IA injection	OMERACT- OARSI responder	Week 12	WOMAC A, B, C and PGA	Ampion, 4 mL
AP-003-B	3	480	101 / 247 / 132	Single IA injection	WOMAC A pain, 5- point Likert scale	Week 12	WOMAC B WOMAC C PGA Rescue analgesia WOMAC A pain with movement, pain at rest	Ampion, 4 mL
Additional Clinical Studies in Support of Safety								
AP-007	1 / 2	47	2 / 23 / 15	Multiple IA injection; 3 injections, every 2 weeks	WOMAC A pain, 5- point Likert scale	Week 20	WOMAC B WOMAC C PGA Physical activity Radiologic changes	Ampion, 4 mL
AP-008	3	342	0 / 114 / 228	Multiple IA injection; 3 injections, every 2 weeks	WOMAC A pain, 5- point Likert scale	Week 20	WOMAC B WOMAC C PGA Physical activity WOMAC A pain with movement	Ampion, 4 mL
AIK	1 / 2	103	33 / 69 / 1	Single IA injection	Pain, 10- point NRS	Day 3, 8, 30 and 84	WOMAC total, parts A, B, C Range in motion Rescue analgesia	Ampion 10 mL, alone or in solution with betamethasone and/or lidocaine and/or saline

In all four well-controlled, single-injection studies, Ampion demonstrated a larger improvement in pain in KL 4 patients compared to saline, indicating a reproducible and consistent response. Analysis of the combined data demonstrate a statistically significant result in this underserved patient population.

In addition to the efficacy analysis described in this section, Ampion has also demonstrated a robust safety profile across the four well-controlled, single-injection studies, as well as the multiple-injection and early phase trials (Table 1.3). No drug-related Serious Adverse Events (SAEs) have been reported in 2,007 patients treated during the clinical development program. The Adverse Event (AE) profile is similar for

Ampion and saline, with a majority of the AEs of minor or moderate severity and unrelated to treatment.

Table 1.3 Summary of Adverse Events

Adverse event (AE)	Overall population		KL 4 population	
	Ampion N=1,076	Saline N=931	Ampion N=475	Saline N=361
One or more AE	381 (35.4%)	386 (41.5%)	150 (30.1%)	140 (38.8%)
One or more related AE	11 (1.0%)	19 (2.0%)	3 (0.6%)	6 (1.7%)
AE by severity*				
Mild	264 (24.5%)	253 (27.2%)	100 (21.2%)	86 (23.8%)
Moderate	162 (15.1%)	190 (20.4%)	58 (12.3%)	74 (20.5%)
Severe	35 (3.3%)	32 (3.4%)	17 (3.6%)	14 (3.9%)
Serious AE (SAE)	15 (1.4%)	20 (2.1%)	5 (1.1%)	7 (1.9%)
AE leading to withdrawal	0 (0%)	0 (0%)	0 (0%)	0 (0%)
AE leading to death	0 (0%)	0 (0%)	0 (0%)	0 (0%)

**Subjects could have AEs in more than one severity category*

CONCLUSIONS

Clinical efficacy observed in previous single-injection studies suggest that Ampion safely relieves pain due to severe (KL 4) osteoarthritis of the knee, the most severe form of OAK, for which there is no FDA approved treatment. Currently, when KL 4 patients are treated for OAK, they are receiving treatment using IA therapy (such as viscosupplementation) that were not studied, nor required in their device approvals to demonstrate efficacy in the KL 4 population ([Rutjes 2012](#)). Historical treatments for OAK pain also involve opioid-based treatments or surgical intervention. Ampion treatment offers clinically meaningful pain relief for an unmet medical need in severely diseased KL 4 patients with a single IA injection.

2 RATIONALE FOR THE STUDY

This is a Phase 3 randomized study designed to confirm the efficacy of an IA injection of Ampion and is designed to support the completed single injection Ampion studies.

2.1 Rationale for the Doses and the Dosing Regimen

This trial will use the 4 mL volume of Ampion used in the single-injection studies (AP-003-A, AP-004, AP-003-B and AP-003-C).

3 STUDY DESIGN

3.1 Study Design Overview

This is a randomized, saline-controlled, double-blind study with a 28-day screening period for each patient followed by a 24-week participation period. This trial will use an adaptive design with promising zone method for sample size re-estimation at the interim analysis. Daily assessments of WOMAC A pain using a subject diary will be assessed for seven days beginning one week prior to the clinic visits at Week 0 (baseline) and Week 12 to allow for calculation of a WOMAC A weekly pain score, which will be used for conducting the primary efficacy analysis.

This trial is designed for 1,034 patients, 517 per study arm, randomized 1:1 for Ampion and saline IA injection. There will be an interim analysis at 724 patients, 362 per study arm, randomized 1:1, Ampion and saline. After the interim analysis, enrollment will either a) continue up to a total of 1,034 patients, 517 patients per study arm, randomized 1:1 for Ampion and saline IA injection; b) allow for sample size re-estimation using the promising zone method (Pocock, 2011) up to 1.5 times the original trial size for a total of 1,552 patients, 776 per study arm, randomized 1:1 for Ampion and saline IA injection.

The clinical effects of treatment on severe OAK will be evaluated at baseline 2, 4, 6, 8, 10, 12, and 24 weeks, using the Western Ontario and McMaster Universities Arthritis Index (WOMAC[®]) osteoarthritis Index 3.1, and the Patient's Global Assessment of disease severity (PGA).

The WOMAC[®] and PGA are validated scoring systems and sets the standard for the patient response. In order not to bias the collection of data, only questions from the validated WOMAC Index 3.1 and the PGA will be asked of patients.

The trial has co-primary hypotheses and requires success on both for a successful trial. First, pain reduction must be demonstrated for Ampion vs. saline control. Next, a function improvement must be shown on Ampion vs. saline control.

The value for clinical benefit is derived from the minimal clinically important improvement (MCII), which is defined as the smallest change that signifies an important improvement to the patient (Tubach 2005). The Initiative on Methods, Measurement, and Pain Assessment in Clinical Trials (IMMPACT) advocates a provisional benchmark of 10-20% for minimally important improvement (Dworkin 2008). In addition, two studies have reported results of a survey of key opinion leaders and clinicians to determine value was best for MCII, suggesting a 20% MCII may be useful in patients with OAK (Tubach 2005), including severe OAK (Salottolo 2018). Clinical benefit will be determined as observed 20% improvements from baseline in pain and function at Week 12 to determine improvements are clinically important and not just statistically significant.

Clinical meaningfulness will be determined by the end results of this trial, specifically by the apparent clinical benefit versus any adverse events or any increased apparent risk. Safety will be assessed by recording adverse events (through 24 hours post-dose and at all follow up contacts) and physical examination and vitals (Baseline, Weeks 6, 12, and 24).

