4 SELECTION OF PATIENTS

4.1 Number of Patients

This trial will use an adaptive design with promising zone method for sample size re-estimation.

This trial is designed for 1,034 patients, 517 per study arm, randomized 1:1 for Ampion and saline IA injection. There will be an interim analysis at 724 patients, 362 per study arm, randomized 1:1, Ampion and saline.

Following the interim analysis, enrollment will either a) continue up to a total of 1,034 patients, 517 patients per study arm, randomized 1:1 for Ampion and saline IA injection; b) allow for sample size re-estimation up to 1.5 times the original trial size for a total of 1,552 patients, 776 per study arm, randomized 1:1 for Ampion and saline IA injection.

The Ampion effect was estimated as the average change in pain from Baseline to Week 12 for KL 4 subjects receiving Ampion from all prior single injection studies randomized 1:1 with saline control. Saline effect was estimated as the average change in pain from Baseline to Week 12 for KL 4 subjects receiving saline from all prior single injection studies randomized 1:1 for Ampion and saline. The sample size for assessing the WOMAC A Pain score alone would be 690 total patients for 90% power.

The Ampion effect was estimated as the average change in function from Baseline to Week 12 for KL 4 subjects receiving Ampion from all prior single injection studies randomized 1:1 with saline control. Saline effect was estimated as the average change in function from Baseline to Week 12 for KL 4 subjects receiving saline from all prior single injection studies randomized 1:1 for Ampion and saline. The sample size for assessing the WOMAC C Function score alone would be 984 patients for 90% power.

The total sample size is chosen as the larger of the two values. To be conservative sample sizes were estimated with a 5% dropout so 1,034 patients will be enrolled to achieve 984 total patients. All ITT patients will be included in the statistical analysis. At the assumed effect size there is a 90% probability of success at 1,034 patients.

The study design of 1,034 total patients achieves 97% power assuming a WOMAC A pain score with mean pain decreases of -0.83 for Ampion and -0.62 for saline and a standard deviation of 0.85.

As described in Section 10, a Promising Zone method will be employed for a sample size re-estimation and the trial may increase to 1,552 patients.

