10.3.4 Statistical Analysis of Co-Primary Effectiveness Endpoints

A mixed-effects model with repeated measures (MMRM) will be used to test the main effect of change in WOMAC A weekly pain score (determined as the average of Daily Pain measurements taken at Baseline and Week 12) from Baseline of Ampion vs. saline at 12 weeks. The model will include change from Baseline measures at 2, 4, 6, 8, 10, and 12 weeks. Treatment assignment, week, and Baseline WOMAC A measure will be included as fixed effects. Patient ID will be included to capture repeated measures using a compound symmetric covariance matrix for residuals. The primary hypothesis test for pain is the change in pain at 12-weeks at the one-sided $\alpha = 0.025$ level.

The same model will be used to test the effect of WOMAC C function change from Baseline of Ampion vs. saline at 12 weeks. WOMAC C will be tested at one sided $\alpha = 0.025$. Because both endpoints have to achieve statistical significance, this pairing ensures the one-sided Type I error control at the 0.025 level.

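### The 20% rule for clinical importance has no saline comparison or stated unit and, for pain, would not separate the arms at mean baselines up to 3.1

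*Protocol*

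**What the plan says.** Protocol 3.1 takes 20% from work on the smallest change that a patient would regard as important, and then sets the rule: "Clinical benefit will be determined as observed 20% improvements from baseline in pain and function at Week 12". Its purpose is "to determine improvements are clinically important and not just statistically significant". The rule names no comparator and no size of between-arm difference. It does not say whether 20% refers to the mean of an arm or to each patient. The next paragraph of 3.1 weighs apparent clinical benefit against adverse events and risk, so the rule bears on the benefit-risk judgement.

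For pain, Protocol 4.1 assumes "mean pain decreases of -0.83 for Ampion and -0.62 for saline and a standard deviation of 0.85". Neither document gives mean changes for function, or a mean baseline for either scale.

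The 20% rule is not among the endpoints in Protocol 3.5 or 10.4, and the SAP does not contain it. SAP 2.3 keeps only the general statement about clinical benefit against risk. SAP 8.6.5 plans CDF plots and an OMERACT-OARSI responder analysis, both exploratory and neither linked to 20%. SAP 10.1 lists no table of patients with a 20% improvement.

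**The concern.** The rule is meant to add something to a significant p-value, namely evidence that the effect is large enough to matter. Change from baseline in a treated arm includes everything that would also have happened after a saline injection. If the saline arm is itself expected to improve by more than 20%, an Ampion arm that is only slightly better will also pass. A small but significant difference could then be called clinically important because of improvement that both arms share. The undefined unit is a second weakness: whether to use arm means or patients could be settled after the data are seen.

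**Working it through.** Changes are written as improvements, so 0.83 stands for a change of -0.83.

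**Inputs.** From Protocol 4.1: improvement 0.83 for Ampion and 0.62 for saline, SD 0.85, 517 per arm. From Protocol 10.3.4: one-sided alpha 0.025. From Protocol 6.1.1: items scored 0 to 4, with 2 moderate and 3 severe. From Protocol 4.3: a screening pain score of at least 1.5. Mean baseline B is not given and is varied.

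**1. Reproduce the plan's own figures.** The plan says: "The sample size for assessing the WOMAC A Pain score alone would be 690 total patients for 90% power". With a difference of 0.83 - 0.62 = 0.21, n per arm = 2 × (1.960 + 1.282)² × 0.85² / 0.21² = 344.3, rounded up to 345, or 690 in total. This agrees exactly. The plan also says: "The study design of 1,034 total patients achieves 97% power" for pain. The calculation gives 97.8% with 517 per arm and 97.2% with 492 per arm (984 in total, after dropout). The pain figures are therefore the ones the design rests on.

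**2. When does an arm mean meet 20%?** It does when improvement ≥ 0.20 × B.
- Saline: B ≤ 0.62/0.20 = 3.1.
- Ampion: B ≤ 0.83/0.20 = 4.15, which covers the whole scale.

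**3. Range of assumed mean baselines.** The last column is Φ((0.62 - 0.20B) / (0.85/√517)), where 0.85/√517 = 0.0374. It takes B as fixed and the assumed saline mean as true.

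| Assumed B | 20% of B | Saline improvement | Ampion improvement | Chance that the observed saline mean meets 20% |
|---|---|---|---|---|
| 1.5 | 0.30 | 41.3% | 55.3% | >0.999 |
| 2.0 | 0.40 | 31.0% | 41.5% | >0.999 |
| 2.5 | 0.50 | 24.8% | 33.2% | 0.999 |
| 3.0 | 0.60 | 20.7% | 27.7% | 0.70 |
| 3.1 | 0.62 | 20.0% | 26.8% | 0.50 |
| 3.5 | 0.70 | 17.7% | 23.7% | 0.02 |
| 4.0 | 0.80 | 15.5% | 20.8% | <0.001 |

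**4. What the rule adds to significance.** In a simple two-sample comparison with 517 per arm, the smallest observed pain difference that is significant is 1.960 × 0.85 × √(2/517) = 0.104. If saline improves by 0.62, an Ampion improvement of 0.62 + 0.104 = 0.724 is just significant. It also meets 20% at any mean baseline up to 0.724/0.20 = 3.62. At the planned effect, saline accounts for 0.62/0.83 = 75% of the Ampion change.

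**5. The patient-level reading.** Assume normally distributed changes with SD 0.85 and every patient at baseline B. The proportion reaching 20% is Φ((improvement - 0.20B)/0.85).
- B = 2.0: saline Φ(0.22/0.85) = 60%, Ampion Φ(0.43/0.85) = 69%.
- B = 2.5: saline Φ(0.12/0.85) = 56%, Ampion Φ(0.33/0.85) = 65%.

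More than half of saline patients pass, so only the difference between the proportions says anything about Ampion.

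**6. Function.** A total of 984 at 90% power implies a standardized difference of (1.960 + 1.282) × √(2/492) = 0.207. The saline change cannot be recovered from that, so the function half of the rule cannot be checked.

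**The case against.** The strongest reply is that the rule does not stand alone. Protocol 3.1 and 10.3.5 require superiority over saline on both pain and function, and 20% comes on top of that. This stands. A reader might infer that the trial would declare clinical benefit in the saline arm too, or that Ampion's benefit could not be shown at all. The documents support neither. The co-primary tests supply the comparison, and the missing piece is a comparative criterion for whether the difference matters.

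Three further points limit the finding:

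- The rule covers pain and function together, and only pain can be checked.
- Mean baseline is unknown, and above 3.1 the assumed saline mean falls short. The entry floor of 1.5 and the description of entry pain as moderate or somewhat worse make baselines below 3.1 plausible, but that is inference.
- The 20% figure derives from a change important to the patient, so a patient-level rule may have been intended. That would suit a comparison of responders, but none is planned.

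A reader might also set the planned difference of 0.21 against 20% of baseline and conclude that the trial is designed for an unimportant effect. The documents do not support that. They define the threshold as improvement within a patient, not as a difference between arm means, and they also cite a 10-20% benchmark.

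Some relevant output is already planned: the CDF plots, the OMERACT-OARSI analysis, and percent change summarised by visit (SAP 8.6.1). None is tied to the 20% rule.

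**Conclusion.** The concern holds in a limited form. The only stated criterion for clinical importance has no comparator and no defined unit. For pain, on the plan's own assumed changes, the saline mean meets it at any mean baseline up to 3.1, so at such baselines it would not separate the arms. It adds little to a significant co-primary result and credits to Ampion change that saline shares.

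The size of this rests on the assumed saline change of 0.62 and on a mean baseline that the documents do not give. Nothing is shown for function. The co-primary tests are unaffected, and the rule is not a formal success criterion. What is weakened is any statement of clinical benefit based on the rule. The change should be made before unblinding, so that the definition is not chosen after the results are known.

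**What to change.** In Protocol 3.1 and in the SAP, state that the 20% threshold applies to each patient. Assess clinical benefit by the Ampion-minus-saline difference, with 95% CI, in the proportion of ITT patients with at least 20% improvement from baseline at Week 12, for pain and for function. Present it beside the planned CDF plots as support to the co-primary tests, not as a replacement. Add the table to SAP 10.1.

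This does not fix how large a difference in proportions is clinically important, but it gives readers a comparative figure on which to judge.

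The cost is protocol and SAP wording and one more table from data already collected. The downside for the sponsor is that the resulting statement of clinical benefit may be less favourable than one based on change from baseline alone.
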